5.2.2.2. Right censored Data

Not applicable.

5.2.2.3. Visit-specific censored Data

Data from visit x will be censored for the PPS analysis under the following conditions.

Code	Condition under which the code is used
270.x/2090.X	Subjects did not comply with blood sample schedule at visit x

5.3. Important protocol deviation not leading to elimination from per-protocol analysis set

Not applicable.

6. STATISTICAL ANALYSES**6.1. Demography****6.1.1. Analysis of demographics/baseline characteristics planned in the protocol**

Descriptive statistics (mean, standard deviation, median, minimum and maximum) for age, height and weight at enrolment will be calculated overall and by vaccine schedule.

Distributions of subjects by sex and ethnic origin will be summarized overall and by vaccine schedule as per parent study assignment.

6.1.2. Additional considerations

In addition to what planned in the protocol, subject distribution by booster visit will be provided per vaccine schedule and overall.

6.2. Exposure

Subjects exposed to vaccination will be those who will receive the second booster dose, only if their values go below 10.

6.2.1. Analysis of exposure planned in the protocol

Not applicable.

6.2.2. Additional considerations

Not applicable.

6.2.3. Efficacy/Effectiveness

Not applicable.

6.2.4. Analysis of efficacy planned in the protocol

Not applicable.

6.2.5. Additional considerations

Not applicable.

6.3. Immunogenicity**6.3.1. Analysis of immunogenicity planned in the protocol**

The primary analysis population for immunogenicity is the per protocol set and if, in any study group, the percentage of subjects with serological results excluded from the PP set is at least 10%, a second analysis will be performed on the FAS. All analyses entail the calculation of summary statistics by vaccination schedule and age stratification, together with their 95% confidence intervals.

Long-term immunogenicity (persistence).

- Percentages of subjects with neutralizing antibody titres ≥ 2 and ≥ 10 as measured by NT assay will be tabulated by vaccine schedule (as assigned from the parent study) together with the associated two-sided 95% Clopper-Pearson confidence intervals (CIs). The vaccine schedule difference in the percentage of subjects with neutralizing antibody titres ≥ 2 and ≥ 10 will be calculated using a binomial distribution. The associated confidence interval for these differences will be constructed using the Miettinen-Nurminen method.
- GMTs with the associated 95% CIs will be computed for each vaccine schedule (as assigned from the parent study), by taking the exponential of the corresponding log10-transformed (least squares) means and 95% confidence intervals, from an ANOVA model with group as fixed factor. Vaccine schedule differences along with 95% CIs will also be computed.

SAS code

The SAS statements to calculate the adjusted GMCs will be similar to:

```
PROC glm;  
  BY vaccinegroup;  
  CLASS group;  
  MODEL log_Ab=group;  
  LSMEANS group / tdiff stderr;  
RUN;
```

Between-group ratios of GMTs will be calculated by including additional SAS statements within PROC GLM, similar to:

```
ESTIMATE 'Group 1 - Group 2' group 1 -1;
```

Subjects with antibody levels below 10 at a given visit (and that will therefore receive a booster dose) will be kept in the analysis of persistence also for the subsequent years with a value imputed to half of the detection limit, i.e. 1.

Analyses will be conducted on the PPS-1 (and repeated on the FAS-1, if appropriate).

Immune response to booster dose (boostability):

- Percentages of subjects with neutralizing antibody titres ≥ 2 and ≥ 10 at 21 days after administration of the booster dose, as measured by NT will be tabulated by vaccine schedule (as assigned from the parent study) together with the associated two-sided 95% Clopper-Pearson CIs.
- GMTs with the associated 95% CIs at 21 days after administration of the booster dose, will be computed for each vaccine schedule (as assigned from the parent study), by taking the exponential of the corresponding log10-transformed (least squares) means and 95% confidence intervals, from an ANOVA model with group as fixed factor.

SAS code

The SAS statements to calculate the adjusted GMCs will be similar to:

```
PROC glm;  
  BY vaccinegroup;  
  CLASS group;  
  MODEL log_Ab=group;  
  LSMEANS group / tdiff stderr;  
RUN;
```

Between-group ratios of GMTs will be calculated by including additional SAS statements within PROC GLM, similar to:

```
ESTIMATE 'Group 1 - Group 2' group 1 -1;
```

- GMRs with the associated 95% CIs after/before booster as measured by GSK Biologicals' NT calculated for each of the different schedule groups.

Computationally, the antibody value as recorded prior to the booster visit (i.e. at the previous scheduled clinic visit) will be considered as the denominator for the calculation of the ratio.

Analyses will be conducted on the PPS-2 (and repeated on the FAS-2, if appropriate).

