### 1.3. Rationale for the study design

Participants of study V48P7E2 will be asked to participate in the current study. The aim of this study is to investigate the persistence of antibody response in adults up to 15 years after one *Encepur Adults* booster dose. Persistence of antibody response will be evaluated based on TBE-NT. Subjects with an NT titre below 10 at enrolment and subjects with a

decrease of NT titre to below 10 during the study will be invited to receive a booster vaccination. Data collected from this study may allow the provision of better information to prescribers who administer *Encepur Adults*, so that they can appropriately adjust the time of booster vaccinations to individuals who received different primary vaccination schedules and who live in TBE endemic regions.

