### 6.5. Contraindications to subsequent vaccination

The following events constitute absolute contraindications to administration of *Encepur Adults*. If any of these events occur during the study, the subject must not receive a dose of vaccine but may continue other study procedures at the discretion of the investigator.

- Anaphylaxis following any previous administration of vaccine.
- Pregnancy (see Section 8.2.1).
- Any condition that in the judgment of the investigator would make intramuscular injection unsafe.

The following events constitute contraindications to administration of *Encepur Adults* at that point in time; if any of these events occur at the time scheduled for vaccination, the subject may be vaccinated at a later date, within the time window specified in the protocol, or withdrawn at the discretion of the investigator.

- Acute disease on the day of booster vaccination (acute disease means moderate or severe illness with or without fever). The vaccine may be administered to subjects with minor illness such as mild diarrhoea or mild upper respiratory tract infection with oral temperature <38.0°C).

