## **10.5. Derived and transformed data**

- Immunogenicity

- The cut-off value is defined by the laboratory before the analysis and is described in Section 5.7.3.
- A seronegative subject is a subject whose titre is below the cut-off value.
- A seropositive subject is a subject whose titre is greater than or equal to the cut-off value.
- The GMTs calculations are performed by taking the anti-log of the mean of the log concentration/titre transformations. Values to be used for the antibody concentrations/titres below the assay cut-off will be described in the Statistical Analysis Plan (SAP).
- Handling of missing data: for a given subject and a given immunogenicity measurement, missing or non-evaluable measurements will be replaced only if values before and after are available. In such an occurrence, the following rule will apply:
  - The missing value will be imputed to be equal to the lowest one between the previous and the subsequent available values (conservative approach).
  - Subjects receiving a booster dose because their NT <10 will be kept in the analysis of persistence until year 15 with an NT imputed value equal to 1.

In case of significant non-compliance of study procedures for reporting symptoms, the analysis plan will be reassessed to ensure more accurate reporting of study data by further analysis.

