### **10.7.2. Statistical Methods for Immunogenicity Variables**

Long-term immunogenicity (persistence).

- Percentages of subjects with neutralizing antibody titres  $\geq 2$  and  $\geq 10$  as measured by NT assay will be tabulated by vaccine schedule (as assigned from the parent study) together with the associated two-sided 95% Clopper-Pearson confidence intervals (CIs). The vaccine group difference in the percentage of subjects with neutralizing antibody titres  $\geq 2$  and  $\geq 10$  will be calculated using a binomial distribution. The associated confidence interval for these differences will be constructed using the Miettinen-Nurminen method.
- GMTs with the associated 95% CIs will be computed for each vaccine schedule (as assigned from the parent study), by taking the exponential of the corresponding log10-transformed (least squares) means and 95% confidence intervals, from an ANOVA model with group as fixed factor. Vaccine schedule differences along with 95% CIs will also be computed.

Subjects with antibody levels below 10 at a given visit (and that will therefore receive a booster dose) will be kept in the analysis of persistence also for the subsequent years with a value imputed to half of the detection limit, i.e. 1.

Analyses will be conducted on the PPS-1 (and repeated on the FAS-1, if appropriate).

Immune response to booster dose (boostability):

- Percentages of subjects with neutralizing antibody titres  $\geq 2$  and  $\geq 10$  at 21 days after administration of the booster dose, as measured by NT will be tabulated by vaccine schedule (as assigned from the parent study) together with the associated two-sided 95% Clopper-Pearson CIs.

- GMTs with the associated 95% CIs at 21 days after administration of the booster dose, will be computed for each vaccine schedule (as assigned from the parent study), by taking the exponential of the corresponding log10-transformed (least squares) means and 95% confidence intervals, from an ANOVA model with group as fixed factor.
- GMRs with the associated 95% CIs after/before booster as measured by GSK Biologicals' NT calculated for each of the different schedule groups.

Computationally, the antibody value as recorded 6 months prior to the booster visit (i.e. at the previous scheduled clinic visit) will be considered as baseline.

All analyses will be repeated for each age subgroup.

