6.3.2. Additional considerations

All analyses will be repeated for each age subgroup.

- To complement the analysis of persistence, a thorough description of NT waning from year 1 after the first booster dose up to 15 years will be presented for the set of subjects completing the entire 15-year follow-up with no protocol deviations, including those receiving a second booster dose within the previous clinical studies and current study; for those ones, a constant value of NT = 1 from the post booster visit will be used in the analysis.
- Analysis of boostability will be presented both by time-point (i.e. for each unscheduled visit separately) and aggregated (i.e. all visits considered together).
- Depending on the amount of missing data and as a form of sensitivity analysis, a repeated measure model could be used to evaluate the GMTs persistence.

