8. CONDUCT OF ANALYSES

8.1. Sequence of analyses

Annual listings reporting subjects NT titres will be produced and made available to the investigators. Every year, any subject whose NT titre falls below 10 will be offered a second booster vaccination with *Encepur Adults*.

Final analysis will be conducted after completion of the immunogenicity evaluation at year 15, when the CSR will be produced.

A clinical study report containing all data will be written at study end.

Description	Analysis ID	Disclosure Purpose (CTRS=public posting, SR=study report, internal)	Dry run review needed (Y/N)	Study Headline Summary (SHS)requiring expedited communication to upper management (Yes/No)	Reference for TFL
Immunogenicity analysis year 11	IMM11y	Internal	N	No	16.2.6.1
Immunogenicity analysis year 12	IMM12y	Internal	N	No	16.2.6.1
Immunogenicity analysis year 13	IMM13y	Internal	N	No	16.2.6.1
Immunogenicity analysis year 14	IMM14y	Internal	N	No	16.2.6.1
Final analysis year 15	Final	Study report	Y	Yes	All tables and listings in the TOC

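### The primary persistence rule sets later titres to 1 by a low titre in Protocol 10.7.2 and SAP 6.3.1, but by booster receipt in Protocol 10.5 and SAP 6.3.2, leaving unboosted subjects with NT below 10 badly covered

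*SAP*

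**What the plan says.** Four places define who is carried forward with NT = 1.

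- **SAP 6.3.1, primary persistence analysis:** "Subjects with antibody levels below 10 at a given visit (and that will therefore receive a booster dose) will be kept in the analysis". From the next year on, each such subject is given the value 1, which is half the assay's lower limit.
- **Protocol 10.7.2:** the same rule, opening "Subjects with antibody levels below 10 at a given visit (and that will therefore receive a booster dose".
- **Protocol 10.5, under the handling of missing data:** "Subjects receiving a booster dose because their NT <10 will be kept in the analysis of persistence until year 15", with the value 1.
- **SAP 6.3.2, waning analysis (also SAP 4.2 and Protocol 10.2):** for subjects given a second booster, "for those ones, a constant value of NT = 1 from the post booster visit will be used in the analysis".

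Elsewhere the booster is not automatic. Protocol 1.3 says that subjects with a "decrease of NT titre to below 10 during the study will be invited to receive a booster vaccination". SAP 8.1 says that "any subject whose NT titre falls below 10 will be offered a second booster vaccination". Protocol 4.2 and 4.3 set extra entry conditions for vaccination, and Protocol 5.7.5 foresees a subject with NT below 10 who has an exclusion criterion against it. For the absolute contraindications in Protocol 6.5, "the subject must not receive a dose of vaccine but may continue other study procedures at the discretion of the investigator". Under Protocol section 3 (text below Table 2), only a subject who receives a booster is released from later scheduled visits.

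**The concern.** A second booster makes later titres uninformative about persistence after the first. That is the reason to impute, and it does not apply to a subject who was never boosted again. Such a subject's later samples measure what the primary objective asks about.

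The word for consequence inside the parenthesis in SAP 6.3.1 presumes that every subject below 10 is boosted. The SAP does not repeat the Protocol 10.5 wording, so a programmer working on the primary persistence tables from the SAP has only the titre-based sentence. Applied literally, it turns an observed value into 1 and makes one reading below 10 permanent. The same unboosted subject could then show a measured titre in the waning table and a 1 in the primary table of the same report.

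**Working it through.** The plan states no figure for this effect, so there is none to reproduce. Two preliminary checks agree: half the detection limit of 2 (Protocol Appendix A) is 1, and the planned group sizes 51 + 46 + 103 (Protocol Table 1) make 200.

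**Step 1: who is affected.** A subject must have NT below 10 at a scheduled visit, receive no second booster, stay in follow-up, and give a later sample. A first reading below 10 at Year 15 does not count, because no scheduled visit follows. A subject revaccinated outside the study may leave the per-protocol set: TBE vaccination other than as indicated is a listed example of a major deviation (Protocol 10.4, SAP 5.1).

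**Step 2: effect per subject.** Replacing a measured titre t by 1 lowers the log10 value by log10(t): 0.301 for t = 2, 0.699 for t = 5, 0.954 for t = 9. It also turns a result at or above 2 into one below 2. The result against 10 stays the same unless t is 10 or more.

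**Step 3: effect per group.** The ANOVA has group as its only factor, so each group's GMT is the anti-log of its mean log titre. With k such subjects among n:

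- GMT multiplier = t^(−k/n)
- fall in the percentage at or above 2 = 100 × k/n points (for t of 2 or more)

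Protocol 4.1 says that the number falling below 10 cannot be estimated, so k and t are assumptions. With k = 2:

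| Group (n) | GMT multiplier, t = 2 | t = 5 | t = 9 | Fall in % at or above 2 |
|---|---|---|---|---|
| R (46) | 0.970 | 0.932 | 0.909 | 4.3 points |
| C (51) | 0.973 | 0.939 | 0.917 | 3.9 points |
| AC (103) | 0.987 | 0.969 | 0.958 | 1.9 points |

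For R with t = 8: 8^(−2/46) = 0.914, a fall of about 9%.

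Over k = 1 to 5 and t = 2 to 9, the multiplier runs from 0.993 (AC, k = 1, t = 2) to 0.788 (R, k = 5, t = 9). The fall in the percentage at or above 2 runs from 1.0 to 10.9 points.

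**Step 4: effect on the interval.** If all 46 R subjects would otherwise be at or above 2, the Clopper-Pearson lower limit is 92.3%. With two of them set to 1 (44 of 46) it is 85.2%.

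**Step 5: rebound.** Each subject whose later titre is back at or above 10 but is set to 1 moves the percentage at or above 10 by 1/46 = 2.2 points in R, 1/51 = 2.0 in C and 1/103 = 1.0 in AC.

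**The case against.** The best defence is that the parenthesis limits the rule to boosted subjects. On that reading all four places agree. Protocol 10.5 helps it by placing the rule under missing data, and both documents speak of imputing a value and keeping the subject in the analysis, which suits people who no longer attend. A reader might infer that the documents flatly contradict each other, or that they order measured data to be overwritten. Neither follows: no sentence says that an observed titre is to be discarded. But on the defensive reading SAP 6.3.1 has no explicit rule for unboosted subjects below 10, so the text still needs repair.

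The affected group is also narrow. The clause on continuing other procedures covers only three absolute contraindications (anaphylaxis after earlier vaccination, pregnancy, unsafe intramuscular injection), at the investigator's discretion. It does not cover the whole booster exclusion list. Subjects who decline, or who meet another exclusion, remain because only booster receipt ends the scheduled visits. This stands as a limit on size, not as an answer.

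Finally, counting any fall below 10 as lasting loss of persistence is a defensible conservative convention, and the study is descriptive. If that is intended, the plan should say so and not reach it through an assumption of universal uptake.

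**Conclusion.** The wording should be corrected. Two places tie NT = 1 to a low titre and presume the booster; two tie it to booster receipt. Read literally, the SAP's primary rule would set measured titres of unboosted subjects to 1 and bias later GMTs and the percentage at or above 2 downward.

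The size is unknown and probably small. The illustrative 3% to 9% fall in the R group's GMT and the 4.3-point fall rest on two assumed subjects with assumed titres of 2 to 8; a titre of 8 is near the top of the possible range.

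A reader might also infer a general downward bias in the percentage at or above 10. The documents do not support that: for a subject who stays below 10, the result is identical under both rules. It changes only on a rebound, and the documents give no assay repeatability from which to judge how often that happens.

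**What to change.** In Protocol 10.7.2 and SAP 6.3.1, replace the parenthesis with an explicit receipt condition matching Protocol 10.5. For example: *Subjects with NT<10 who receive a second TBE booster will have NT=1 imputed at scheduled visits after that booster; for NT<10 subjects not boosted, measured titres are used.* Simply deleting the parenthesis would make matters worse, since those are the only words there that link the rule to a booster.

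The cost is one sentence in each document. No new data are needed, because Protocol Table 4 already schedules the samples, and clinical management is untouched.

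There is one small downside: two subjects with the same low titre would later be handled differently according to booster receipt. Reporting the titre-triggered version as a sensitivity analysis would show whether this matters.

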### 5.7.5. Immunological correlates of protection

#### Neutralization assay:

The presence of circulating antibodies to the virus at or above locally agreed concentrations (for example, an NT titre of  $\geq 10$ , evaluated with the Holzmann NT, Vienna) is commonly considered to be a surrogate marker of protection [WHO, 2011b]. However, systematic clinical studies that substantiate this assumption are not available [WHO, 2011b].

According to the test procedure of the GSK Biologicals' NT, the lower limit for detectable neutralizing TBE antibodies is a titre of 2. The lower working range is defined by technical conditions, since the lowest starting dilution is a 1:2 dilution). In order to identify a clinically meaningful threshold of NT titre for GSK in-house NT, an evaluation of TBE NT antibody titres in 19 subjects with evidence for a naturally acquired TBE immunity was performed [Zent, 2004]. This approach was based on the following consideration: TBE disease is assumed to provide a life-long lasting immunity. That is, no reports of re-occurrence of TBE disease have been reported to date.

Therefore, it can be assumed that antibody titres in subjects with a naturally acquired TBE immunity, but without manifest TBE disease are clinically meaningful. Retrospective analysis of basic NT titres of 19 subjects who tested TBE NT positive prior to their 1st TBE vaccination revealed an NT titre of approximately 10 as a lower confidence limit of the GMT (NT). Therefore, a titre of 10 has been considered as a more conservative threshold than 2 for interpretation of results of the GSK Biologicals' in-house NT.

The investigator is encouraged to share the immunological assay results for non-responders with the study subjects/subjects' parent(s)/LAR(s).

For the subjects identified as non-responders, it remains the responsibility of the investigator in charge of the subject's clinical management to determine the medical need for re-vaccination and to re-vaccinate the subjects as per local/regional practices.

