## 10. STATISTICAL METHODS

### 10.1. Primary Endpoint(s)

The immunogenicity endpoints will be based on the TBE NT antibody levels in serum at year 11, 12, 13, 14 and 15 as measured by GSK Biologicals' NT.

Measures of immunogenicity are:

- Percentages of subjects with detectable TBE Neutralizing Antibody Titres  $\geq 2$  and  $\geq 10$  as measured by GSK Biologicals' NT.
- Geometric Mean Antibody Titres as measured by GSK Biologicals' NT calculated for each of the different schedule groups.

Endpoints will be summarized according to the immunization schedule received in the V48P7E1 study and further detailed by the following age subgroups: 25 to 49 years,  $\geq 50$  years and  $\geq 60$  years.

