**APPENDIX A    LABORATORY ASSAYS**

The TBE-virus neutralization test (TBE-NT) is a functional assay that detects in human serum neutralizing antibodies that are directed against TBEV.

Heat-inactivated sera are serially diluted 2-fold in 96well microtiter plates and incubated with equal volumes of TBE-virus (isolate K23). Each dilution is tested 4-fold in a human lung carcinoma cell line (A549) for infectious TBE-virus. After incubation the cell layers in each well are screened microscopically for cytopathic effects. The neutralizing antibody titer is expressed as the neutralizing dose that protects 50% of the cell cultures calculated according to Kaerber.

The serum starting dilution is 1:2. Seropositivity is defined as a titer of  $\geq 2$  (lower limit of detection: titer of 2).

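### Imputing NT = 1 after a titre below 10 counts subjects last measured at 2 to 9.9 as undetectable in the primary % ≥2 and GMT; no committed analysis omits it, and the rule as worded also reaches unboosted subjects

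*SAP*

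**What the plan says.** Protocol 10.1 sets three primary measures: % with titre ≥2, % with titre ≥10, and GMT by schedule. They "will be based on the TBE NT antibody levels in serum at year 11, 12, 13, 14 and 15".

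One imputation rule serves all three, but it is worded in two ways:

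- Protocol 10.5: "Subjects receiving a booster dose because their NT <10 will be kept in the analysis of persistence until year 15", with the value 1.
- Protocol 10.7.2: "Subjects with antibody levels below 10 at a given visit (and that will therefore receive a booster dose) will be kept" in the later years with the value 1. SAP 6.3.1 repeats this: such subjects are "kept in the analysis of persistence also for the subsequent years with a value imputed to half of the detection limit, i.e. 1".

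Protocol 5.7.5 states that "the lower limit for detectable neutralizing TBE antibodies is a titre of 2", and Appendix A agrees ("lower limit of detection: titer of 2"). Protocol 10.5 adds: "A seropositive subject is a subject whose titre is greater than or equal to the cut-off value".

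The trigger is therefore 10, while the cut-off for detectability is 2. The booster is offered, not mandatory (SAP 8.1). A subject who meets an exclusion criterion for vaccination does not get it in the study (Protocol 5.7.5, note). Only subjects who receive it are released from later scheduled visits (Protocol 3). The NT-waning description (SAP 4.2 and 6.3.2) also uses the value 1. The repeated-measures model in SAP 6.3.2 is optional, depends on the amount of missing data, and is not said to leave the imputed values out.

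**The concern.** A subject measured at, say, 7 is seropositive by the protocol's own definition in that year. In every later year the same subject is tabulated as below the detection limit, although no sample was taken to show it. The endpoint is defined on antibody levels in serum, and neither document gives a composite definition that would justify the 1.

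Two primary measures lose part of their meaning. % ≥2 comes close to the share that stayed at or above 10 at earlier visits, so it says little about detectability. The GMT depends on a chosen constant, and the spread behind its confidence interval widens. The study aims to describe antibody kinetics and to inform the timing of a second booster (Protocol 1.2), so these curves are the result.

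Separately, 10.7.2 and 6.3.1 assume that everyone below 10 is boosted. Read literally, they replace real later titres of subjects who decline or are ineligible.

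**Working it through.** **Inputs from the documents.** Detection limit 2; trigger NT <10; approximate group sizes C 51, R 46, AC 103 (Protocol Table 1; 51 + 46 + 103 = 200). NT <10 in V48P7E2 is an exclusion (Protocol 4.3), so entrants start at 10 or above. The imputed value reproduces: 2 / 2 = 1.

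**Not in the documents.** The share f imputed at a visit and the last titre t. Protocol 4.1 and Table 3 say the number falling below 10 cannot be estimated. Both are assumptions below.

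**Closed form, compared with the last measured titre.** If all imputed subjects were last at 2 to 9.9:

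- % ≥2 falls by f.
- GMT multiplier = t^(−f). Example: t = 5, f = 10% gives 5^(−0.10) = 0.851, or 14.9% low.

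| f | GMT low by, t = 2 | GMT low by, t = 9.9 |
|---|---|---|
| 1% | 0.7% | 2.3% |
| 5% | 3.4% | 10.8% |
| 10% | 6.7% | 20.5% |
| 13% | 8.6% | 25.8% |

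A subject whose last titre was below 2 does not change % ≥2. The effect on GMT then depends on how such titres are coded. Protocol 10.5 leaves that to the SAP ("Values to be used for the antibody concentrations/titres below the assay cut-off will be described in the Statistical Analysis Plan"), which gives no general rule.

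**Group scale.** One imputed subject costs 1/51 = 2.0 points of % ≥2 in C, 1/46 = 2.2 in R and 1/103 = 1.0 in AC. Five imputed in C turn 51/51 = 100% (Clopper-Pearson 95% CI 93.0–100) into 46/51 = 90.2% (78.6–96.7).

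**Simulation at Year 15.** 400,000 subjects per scenario, entry requires a measured titre ≥10 at Year 10, and everyone who falls below 10 is imputed afterwards. All titre inputs are assumed. Each result cell shows as measured → under the rule.

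| GMT, log10 SD, assay SD, decline per year | f | % ≥2 | GMT | log10 SD | % ≥10 |
|---|---|---|---|---|---|
| 150, 0.4, 0.15, 5% | 0.7% | 100 → 99.3 | 117.2 → 115.0 | 0.424 → 0.451 | 99.5 → 99.0 |
| 100, 0.4, 0.15, 5% | 2.1% | 100 → 97.9 | 79.3 → 75.3 | 0.417 → 0.483 | 98.8 → 97.4 |
| 60, 0.5, 0.15, 5% | 7.6% | 100 → 92.4 | 54.1 → 45.3 | 0.469 → 0.633 | 95.3 → 91.0 |
| 60, 0.5, 0.2, 10% | 13.4% | 99.9 → 86.6 | 41.5 → 30.6 | 0.488 → 0.714 | 90.2 → 83.6 |

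The GMT is about 2% to 26% low (1 − 115.0/117.2 = 1.9%; 1 − 30.6/41.5 = 26.3%). % ≥10 is 0.5 to 6.6 points low. With assay noise set to zero, f in these scenarios drops to 0.2–6.1%.

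**Separate check** (Year 10 GMT 100, log10 SD 0.5, decline 0.04 log10 per year). Without noise, Year 15 % ≥2 is 100.0 as measured and 97.6 under the rule, exactly the Year 14 % ≥10. % ≥10 is 96.8 either way, and the GMT is 67.4 against 64.2. With assay noise of 0.15 log10, % ≥10 is 96.1 as measured and 93.7 under the rule.

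**The case against.** The rule is pre-specified, stands in both documents and errs downward, so it cannot overstate persistence. Protocol 10.5 places it directly after an imputation rule described as conservative. No hypothesis is tested (Protocol 10.9, SAP 7). The threshold treated as clinically meaningful is 10, and 2 is a technical limit (Protocol 5.7.5). Few events may occur: the protocol reports above 90% at or above 10 for at least 10 years, and entry excludes NT <10 in the previous study. All of this stands. It limits the consequence but does not make an unmeasured 1 an antibody level.

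Other planned outputs do not close the gap. Annual listings and the separate analysis of boosted subjects (Protocol Table 3) leave the primary tables as they are, and the FAS analysis follows the same rule.

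A reader might infer that the rule is simply right for % ≥10. It is interpretable there, as at or above 10 now and never measured below 10 at an earlier visit. With assay noise, however, some subjects would measure ≥10 again, so the tabulated figure lies below the measured one.

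A reader might also infer that carrying the last titre forward should replace the rule. For % ≥2 that returns about 100% almost by construction, so it cannot show later loss of detectability.

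**Conclusion.** The concern holds, as a matter of reported estimates and not of a test. For Years 12 to 15 the rule lowers the primary % ≥2 by the share of subjects imputed from a detectable titre, and lowers the GMT by the factor t^(−f). The size cannot be fixed from the documents. Over the assumed scenarios it runs from negligible (f = 0.7%, GMT 2% low) to material (f = 13.4%, GMT 26% low). Within a schedule the direction is always down. Differences between schedules also shift if one schedule has more imputed subjects. % ≥10 remains usable if labelled for what it is.

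The conflict between Protocol 10.5 (boosted subjects) and Protocol 10.7.2 / SAP 6.3.1 (everyone below 10) stands whatever the size.

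Three stronger readings are not supported:

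- A ranking of the alternatives by accuracy. It depends on the assumed noise and a common rate of decline. With varying slopes, carry-forward runs from 1.0% low to 4.6% high in GMT, not uniformly low.
- A case against left-censoring at 10. It rests on subjects returning to ≥10, and with no assay noise none do.
- A fault in the SAP's mention of second boosters in earlier studies. No one was vaccinated in V48P7E2 and NT <10 there is excluded, so it may apply to no enrolled subject.

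**What to change.** 1. **Scope.** In Protocol 10.7.2 and SAP 6.3.1, limit the imputation to subjects who actually received the second booster, as Protocol 10.5 does. Use later titres of unboosted subjects as measured.
2. **GMT.** In SAP 6.3.2, commit to the repeated-measures model on measured pre-booster titres only, including the titre that triggered the booster, and treat post-booster values as missing. Report the NT = 1 result beside it as the worst case.
3. **% ≥2.** Report two bounds: NT = 1 (lower) and last pre-booster titre carried forward (upper). State that the upper bound cannot show later loss of detectability. Present the NT-waning description both ways too.
4. **% ≥10.** Keep the rule, labelled as a composite: titre ≥10 at the visit and no second booster given for an earlier titre below 10.

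The cost is wording in both documents, a few extra tables and some lines of programming, with no new data. The downsides are that carry-forward ignores further waning, and that the model assumes post-booster values are missing at random given the measured titres. That is reasonable when a measured titre triggers the booster, but it should be stated.
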